#### **8.3.3.** Cumulative costs and cost rates

Cumulative costs will be visualized spanning the baseline and exposure periods via mean cumulative function step curves (with a grey zone corresponding to the 95% confidence interval)(Nelson 1998; 2000; Blackstone and Rajeswaran 2019). A marked increase in the cumulative cost slope is expected at T0, corresponding to the initiation of mepolizumab. However, the cumulative cost slope is hypothesized to later decrease at a currently unknown time point after T0 due to reduced health resource consumption in other sectors and is of interest. The cost rate curve (ie the slope of the mean cumulative cost curve) will be determined by a 28-day sliding window for the demonstration of changes in the speed of accumulating costs. Mean cumulative functions describing the difference between baseline and exposure periods can be computed (Nelson 2000). For the latter, the elapsed time at which the 95% confidence interval no longer contains zero indicates differences in cumulative costs. Similarly, mean cumulative functions for events of interest (specific health resource usages or associated costs found to differ before versus after T0) can be computed.

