### 1.2. Benefit/Risk Assessment

This study will be performed exclusively using French national claims database data (SNDS). As a non-interventional study based on secondary use of of medico-administrative data, it meets requirements for a 'European Network of Centers for Pharmacoepidemiology and Pharmacovigilance (EnCEPP) study'. Safety-relevant results will be presented as aggregated data only.

The reader should note that the current knowledge on mepolizumab indicates a list of quite minor side effects (injection site reactions, lower respiratory tract infections, urinary infections, pharyngitis, headache, back pain, and others as mentioned in the Summary of Product Characteristics). Compared with the long-term use of oral corticosteroids (OCS) or short acting beta antagonists (SABA) (currently the most-used anti-asthma medications)(Nwaru et al. 2020), whose side effects include adrenal insufficiency, diabetes, and increased mortality (Zazzali et al. 2015; Sweeney et al. 2016; Barry et al. 2017; Zeiger et al. 2017; Daugherty et al. 2018; Sullivan et al. 2018; Nwaru et al. 2020), mepolizumab initiation is hypothesized to not only decrease the costs associated with recurrent severe asthma, but also costs purportedly due to the comorbid burden associated with rescue medicine.

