## Drug consumption

All drug consumption will be analyzed, with specific attention given to (i) mepolizumab, (ii) corticosteroids (oral/IV/systemic, inhaled, topical, etc), asthma-specific medications (selective beta-2-adrenoreceptor agonists, adrenergics in combination with corticosteroids or other drugs, anticholinergics, adrenergics for systemic use, xanthines, leukotriene receptor antagonists, other systemic drugs for obstructive airway diseases, etc), and diabetes-related medications (buiguanides, insulin, etc). Drugs demonstrating significant changes in cumulative dose between the baseline and exposure periods (if any in addition to mepolizumab) will be identified.

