### Subpopulations of interest

Sub populations of interest and subject to comparative analyses include sex, age groups, beneficiaries with versus without indicators of severe asthma, uncontrolled asthma, chronic obstructive pulmonary disease, and diabetes (identified via the prescription of specific drugs, hospitalization diagnoses, assessments or combinations thereof).

Objectives	Endpoints
Primary	
To estimate the change in associated costs for the first year of treatment	
 
Total health care costs for the year preceding the initiation of mepolizumab, as well as for the year after.
 

Secondary	
To describe the initial one-year changes in health resource use before and after the initiation of mepolizumab treatment	
 
Cumulative estimates for health resource use and associated costs for the year preceding the initiation of mepolizumab, as well as for the year after.
 

Tertiary/Exploratory	
To further characterize rates of change in health resource usage and/or costs in subpopulations of interest	
 
Sub populations of interest and subject to comparative analyses include sex, age groups, beneficiaries with versus without indicators of severe asthma, uncontrolled asthma, chronic obstructive pulmonary disease, and diabetes (identified via the prescription of specific drugs or combinations thereof).
 

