# 3. Study Design

## 3.1. Overall Design

This retrospective, non-interventional (not involving human subjects) database study will compare real-life patient health resource consumption before versus after a first injection of mepolizumab. Data concerning patients receiving mepolizumab will be collated for a 12-month period (the "baseline period") preceding a first index treatment (at "T0") and compared to a 12-month period occurring after the index treatment (the "exposure period")(Figure 5-1).

[figure not shown]

Figure 3-1 Graphic presentation of the basic study design comparing health care resource use data between a one-year baseline period and a one-year exposure period after the first administration of mepolizumab (T0).

The expected correspondence to calendar time (Figure 5-2) is an inclusion period for T0 starting in February 2018 to December 2018, with 12 months of "follow-up" corresponding to the year 2019. It follows that baseline data will reach back to February 2017. If data for exposure periods longer than 12 months are available, these will also be collected to describe future trajectories of health resource use in as much as possible.

Figure 3-2 The expected correspondence with real time is an inclusion period covering patients who started mepolizumab in the year 2018, with 12 months of "follow-up" in the year 2019.

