#### 4.1. Inclusion Criteria

- Beneficiary in the anonymous French national SNDS database
- The beneficiary received mepolizumab

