### 4.2. Exclusion Criteria

- Health resource use data covering the 12 months preceding the first filled prescription for mepolizumab are not available
- Health resource use data covering the time period starting at the first filled prescription for mepolizumab and ending at subsequent death or at 12 months later are not available

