#### 8.3.4. Potential covariates/subgroups

Subgroups of interest include:

- Demographic groupings: age categories, sex.
- Patients who decrease their consumption of rescue and/or controller medications during the follow-up period versus those who do not.
- Comorbidity groupings: COPD, diabetes

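### Prior use of another asthma biologic in the baseline year is neither restricted nor separated, so the before-after cost change may mix adding a drug with replacing one

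*Protocol*

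**What the plan says.** **Who enters.** Beyond membership of the database, Protocol section 4.1 has one condition: "The beneficiary received mepolizumab". The exclusions in section 4.2 concern data coverage only. The first applies where "Health resource use data covering the 12 months preceding the first filled prescription for mepolizumab are not available", and the second is the equivalent for follow-up. There is no condition on earlier biologic treatment.

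**What is compared.** Section 3.1 sets out to "compare real-life patient health resource consumption before versus after a first injection of mepolizumab", so each patient's own prior year is the only comparator. The primary endpoint (objectives table, section 2) is "Total health care costs for the year preceding the initiation of mepolizumab, as well as for the year after". Section 8.3.2 compares the two years with paired tests.

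**How costs and patients are divided.** Section 2, Costs, names four levels: all costs, mepolizumab, asthma-specific care, and key comorbidities. The subpopulations in section 2 are sex, age, and indicators of severe asthma, uncontrolled asthma, COPD and diabetes. Section 8.3.4 lists age and sex, change in rescue or controller medication, and "Comorbidity groupings: COPD, diabetes". Neither list mentions prior biologic use, and nor do the limitations in section 1.3.

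**How the change is to be read.** Section 1.1 speaks of cost changes attributable to mepolizumab, and section 2 hypothesises that the drug lowers resource use. Section 1.2 frames the contrast as "Compared with the long-term use of oral corticosteroids (OCS) or short acting beta antagonists (SABA) (currently the most-used anti-asthma medications". Section 8.3.3 states that "A marked increase in the cumulative cost slope is expected at T0, corresponding to the initiation of mepolizumab", and then hypothesises a later fall in slope from lower consumption elsewhere.

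**The concern.** The rationale and the expected cost curve describe a patient who adds an expensive drug to steroid and reliever care. The eligibility rules also admit a patient who stops one biologic and starts mepolizumab. For that patient the before-after difference compares two biologics, which is a different question.

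Pooling the two has two effects. The rise in total cost is smaller than it would be in patients adding the drug. In addition, the earlier drug's cost disappears from the non-mepolizumab costs, and from the asthma-specific costs if it was counted there. Under the attribution in sections 1.1 and 2, that disappearance could be reported as care saved by mepolizumab when it is drug substitution.

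**Working it through.** **The plan's own figure.** Section 8.1 gives 29 × 97 = 2813 patients and at least 90% power for effect sizes above 0.063 at two-sided alpha 0.05. At n = 2813 and d = 0.063, the paired t-test (noncentral t, noncentrality d√n) has 91.6% power. The paired Wilcoxon test, taken at efficiency 0.955, has 90.4%. The effect size giving exactly 90% is 0.0611 (t) or 0.0625 (Wilcoxon). The stated figure reproduces. It concerns random error and gives no protection against a mixed baseline.

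**Inputs for the size.** None of these is in the documents, so all are assumptions:
- M = yearly cost of mepolizumab, left as the unit
- s = share of patients who used another asthma biologic in the baseline year and stopped it by T0
- r = that drug's yearly cost relative to M, taken as 0.5 to 1.5
- f = fraction of the baseline year on it, taken as 1 (the upper end)
- g = true saving in other care, set to 0 to isolate the artefact

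**Formulas.**
- Mean change in total cost = M − g − s·r·f·M
- Mean change in non-mepolizumab cost = −g − s·r·f·M

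**Results with g = 0 and f = 1.**

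| s | Apparent fall in non-mepolizumab cost (r = 0.5 to 1.5) | Pooled rise in total cost |
|---|---|---|
| 0 | 0 | 1.00 M |
| 10% | 0.05–0.15 M | 0.95–0.85 M |
| 30% | 0.15–0.45 M | 0.85–0.55 M |

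Example: s = 30%, r = 1.5 gives 0.30 × 1.5 × 1 × M = 0.45 M, and 1.00 M − 0.45 M = 0.55 M.

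Part-year use scales these down in proportion. With f = 0.5 the apparent fall is 0.025–0.075 M at s = 10% and 0.075–0.225 M at s = 30%.

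**By stratum.** At r = 1, f = 1 and g = 0, naive patients show +1.00 M and switchers M − M = 0. At s = 30% the pooled mean is 0.70 × 1.00 M + 0.30 × 0 = 0.70 M, which describes neither group.

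**Against the plan's detectable effect.** With r = f = 1 the shift is s·M. It equals 0.063 SD when s = 0.063 × SD/M. That is 3.15%, 6.3% or 12.6% if the SD of the cost change is 0.5 M, 1 M or 2 M (assumed).

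**Effect on the cost curve.** A biologic stopped at T0 raises the slope before T0 and so shrinks the jump at T0. It leaves the slope later in the exposure year unchanged.

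**The case against.** The strongest reply is that the premise is not in the protocol. No section mentions another asthma biologic, switching or a drug price. The drug list includes "other systemic drugs for obstructive airway diseases" but names no biologic, so placing other biologics in that class is an inference. This stands: the share could be zero, and the size can only be given as a range.

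It can also be said that the primary endpoint is total cost from the payer and collective perspectives in an exhaustive population, and that a discontinued drug is a real budget change. This stands too, and the all-patient result should be kept. What remains is the attribution of that change.

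There are partial safeguards. Hospital stays, consultations and assessments are compared as counts, which a drug's price cannot alter. All drug consumption is analysed, and drugs with significant dose changes are to be identified (section 2, Drug consumption; section 5.7). A large fall in an earlier biologic may therefore be noticed. Noticing it does not split the primary contrast or take its cost out of the other cost levels.

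Finally, the subgroup list in section 8.3.4 is headed as potential, and a statistical analysis plan could add to it. Eligibility and the cost levels are nevertheless set in the protocol, and Appendix 3 (Data Management) requires the variables to be listed in advance.

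A reader might go further and infer two things that the documents do not support:
- That switching would produce the later decline in slope hypothesised in section 8.3.3. It only reduces the jump at T0.
- That patients who later leave mepolizumab for another biologic would distort the primary result in the opposite direction. If the two drugs cost about the same, total cost is about unchanged; only a non-mepolizumab subtotal moves. Persistence and days covered are already measured.

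**Conclusion.** The point holds as one of attribution, conditional on switching. The protocol neither requires a baseline year free of other asthma biologics nor separates patients who used one, while its rationale and expected cost pattern assume the drug is added. If switchers are present, the rise in total cost is reduced by s·r·f·M, and the same amount appears as a fall in non-mepolizumab cost with no change in care.

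The tabulated range rests wholly on assumed shares, prices and a full baseline year on the earlier drug. The documents do not show that the effect is present, and they do not invalidate the all-patient total as a payer budget figure. The change is still worth making because the protocol as written cannot tell substitution from reduced care in its cost contrasts.

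**What to change.** In sections 8.3.2 and 8.3.4:
1. Flag each patient by whether another asthma biologic was dispensed in the 12-month baseline. Name the products or codes in the variable list, and define biologic-naive as no such dispensing in that year.
2. Report the primary and secondary cost contrasts for biologic-naive patients beside the all-patient result.
3. Show other-biologic cost as its own line in both periods, so that it is not counted as saved care.

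The cost is one extra classification from drug data already within the required baseline window. No patient is excluded. The flag shares the limit that section 8.3.1.1 acknowledges for mepolizumab: a drug given during a hospital stay may not be captured.

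The naive stratum has (1 − s) × 2813 patients. At the same SD its intervals are wider by 1/√(1 − s). That is about 5% at s = 10% (2532 patients) and about 20% at s = 30% (1969 patients).

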### Describing the population

The index date "T0" is defined as the day upon which the beneficiary received a first dose of mepolizumab. Population characteristics will be tabulated at this time point and will include age, gender, area and region of residency, universal medical coverage status, and complementary health insurance status.

The population will be further described by providing the duration of treatment with mepolizumab (ie medication persistence (Cramer et al. 2008), defined as date of last administration – T0 in days) as well as the proportion of days of follow-up covered (PDC) by mepolizumab. The current authorized dosage for mepolizumab is a single 100 mg subcutaneous injection every 4 weeks (with an authorized leeway of +- 7 days), and the PDC will be determined accordingly.

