#### Costs

Cumulative per-beneficiary costs (including all health care resource uses and government benefits) will be described and contrasted between the baseline and exposure periods. This will be performed at several levels: (i) all costs regardless of source or potential link with diagnoses, (ii) costs due to mepolizumab, (iii) costs that can be associated with asthma-specific care, (iv) costs that can be associated with the monitoring and care for certain key comorbidities (diabetes, bone density/osteoporosis).

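### The total-cost rate curve will show a short artificial peak and drop soon after T0, so a slowing in other care should be read from a rate curve without mepolizumab costs

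*Protocol*

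**What the plan says.** Section 8.3.3 of the protocol plots mean cumulative cost across the baseline and exposure periods and takes its slope as a cost rate. That rate "will be determined by a 28-day sliding window for the demonstration of changes in the speed of accumulating costs". Two features are expected. The first is at the start: "A marked increase in the cumulative cost slope is expected at T0, corresponding to the initiation of mepolizumab". The second comes afterwards: "cumulative cost slope is hypothesized to later decrease at a currently unknown time point after T0 due to reduced health resource consumption in other sectors".

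Two statements in section 2, under Describing the population, fix the timing of drug costs. T0 "is defined as the day upon which the beneficiary received a first dose of mepolizumab". The authorised regimen is described as a "single 100 mg subcutaneous injection every 4 weeks (with an authorized leeway of +- 7 days".

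Section 2, under Costs, lists separate cost levels, including "ii) costs due to mepolizumab, (iii) costs that can be associated with asthma-specific care", alongside all costs together. Section 8.3.1.3 points to the curves of section 8.3.3 for total costs and says that sub-costs will follow the same strategies. The protocol does not say whether the window is trailing, centred or leading. It does not explicitly provide for a rate curve that leaves mepolizumab out.

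**The concern.** Each mepolizumab dispensation enters the data as a lump on one day. The first lumps are perfectly aligned across patients because T0 is defined by them; the second lumps are not, because the interval may vary. As a 28-day window slides past the first doses, it loses all of them in a single day. Just before, it holds everyone's first dose plus the early second doses. Just after, it holds only the second doses given so far. The rate rises and then falls although nobody has stopped treatment and no other care has changed.

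The curve is the plan's display for seeing when cost accumulation slows, and the plan attributes the slowing to other care. An abrupt early fall produced by drug-cost timing could be misread as such a change, or misdated.

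**Working it through.** The protocol gives no figure for the cost rate, so there is none to reproduce.

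**Inputs from the protocol**
- Window width: 28 days (section 8.3.3). Alignment: not stated.
- First dose: day 0 for every patient (section 2).
- Interval: 28 days, with 7 days of leeway either way, so 21 to 35 days (section 2).

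**Assumptions, because the protocol gives no figures**
- Spread of actual intervals: several shapes tried.
- Mepolizumab share of cost after T0: 30% to 90%, with other costs flat.
- No discontinuation.

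**Drug cost rate, trailing window, in doses per 28 days (steady state = 1.00)**

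Day 27 (window covers days 0 to 27): 1 + P(interval < 28).

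Day 28 (window covers days 1 to 28): P(interval ≤ 28).

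The one-day drop is the difference, 1 − P(interval exactly 28).

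With intervals uniform on the 15 days from 21 to 35:
- day 20: 1.00
- day 27: 1 + 7/15 = 1.47
- day 28: 8/15 = 0.53
- day 31: 11/15 = 0.73
- day 35: 15/15 = 1.00

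The drop in the drug component is (1.467 − 0.533)/1.467 = 64%. A simulation of 100,000 patients agrees.

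**Other interval shapes**

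| Intervals | Day 27 | Day 28 |
|---|---|---|
| Exactly 28 days | 1.00 | 1.00 |
| SD 3 days, cut at 21 to 35 | 1.43 | 0.57 |
| Uniform around a mean of 30 days | 1 + 5/15 = 1.33 | 6/15 = 0.40 |

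**Centred window.** The same curve shifts about two weeks earlier. The rise begins about two weeks before T0, the peak of 1.47 is at day 14, and the fall to 0.53 is at day 15.

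**Second wave.** If each interval runs from the previous actual dose, the third dose falls on the sum of two intervals. At day 48 the trailing window holds all second doses plus the third doses given by then: 1 + 28/225 = 1.12. At day 63 it lacks the third doses still to come: 1 − 28/225 = 0.88. So the wave is about 12% either way, and after day 120 the simulated curve stays within 0.98 to 1.02. If doses instead keep to a fixed calendar with 7 days of leeway, there is no second wave.

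**Total cost.** With drug share s, rate = s × drug rate + (1 − s), from the uniform case:

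| Share s | Day 27 | Day 28 | One-day drop |
|---|---|---|---|
| 30% | 1.14 | 0.86 | 25% |
| 50% | 1.23 | 0.77 | 38% |
| 90% | 1.42 | 0.58 | 59% |

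**Other window widths under exact 28-day dosing.** A 14-day window swings between 0.00 and 2.00 all year, and a 30-day window between 0.93 and 1.87. The 28-day window is flat.

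**The case against.** The strongest reply is that 28 days is the right width. That stands: it cancels the regular dosing cycle, which windows of 14 or 30 days do not. A reader might infer that matching the window to the dosing interval causes the artefact. The exact-dosing case rules that out. The cause is aligned first doses combined with variable later ones.

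Second, the pattern does not resemble what the plan is looking for. The protocol expects a later decrease and nowhere places it at week 4. A dip that recovers in about a week neither imitates nor hides a lasting decrease over 12 months. This also stands, and it limits the risk to about the first 5 weeks.

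Third, the size depends on figures that the protocol does not give. If half of the intervals were exactly 28 days and the rest uniform, the drug swing would halve to about 1.23 and 0.77. At a 50% share that is 0.5 × 1.23 + 0.5 = 1.12 and 0.5 × 0.77 + 0.5 = 0.88 on total cost: smaller, but still a step.

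Fourth, alignment may be left to an analysis plan that is not shown, and the protocol already separates mepolizumab costs. Both are fair. But section 8.3.3 does not tie its search for slowing in other care to a curve without the drug, and that is what would prevent the misreading.

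**Conclusion.** The point holds as a limited one about a descriptive display. With variable intervals, the total-cost rate curve has an edge artefact one window length after the first doses enter: days 27/28 if trailing, about day 14 if centred. With uniform intervals on 21 to 35 days and a drug share of 30% to 90%, total cost falls by 25% to 59% in one day with no change in care, and recovers by day 35. A weaker wave near days 48 and 63 follows only if leeway accumulates.

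Two stronger readings are not supported. The 64% fall belongs to the drug component alone, whereas the planned curve is for total cost. Nor is any result biased: no test is attached to the rate curve, and the cumulative totals, mean cumulative functions, period differences and paired tests are unchanged. Early discontinuation, which would deepen the drop, was not modelled.

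**What to change.** In section 8.3.3:
- keep the 28-day window and state its alignment;
- add a cost rate curve that excludes mepolizumab costs, obtained by subtracting a cost level that section 2 already lists;
- say that any slowing in other care will be identified and dated from that curve;
- say that changes in the total-cost rate in about the first 5 weeks after T0 will not be interpreted as changes in care.

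The cost is one more curve and slightly more programming. The added curve contains none of the drug-cost lumps. Care billed on injection days, such as nursing visits, could leave a trace of the same pattern.

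Two alternatives are weaker because they blur the step expected at T0. Spreading each dispensation over 28 days before applying the window makes the step a ramp that starts at 1/28 = 0.04 on day 0. An 84-day trailing window starts at 28/84 = 0.33 and still drops from 1.16 to 0.84 at days 83/84.
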